3.2.3. Other Efficacy Endpoints

Combination Comparison Phase (ie, through Week 12)

- Endoscopic healing at Week 12 (Mayo endoscopic subscore of 0 or 1).
- Normalization of endoscopic appearance of the mucosa (Mayo endoscopic subscore of 0).
- Histologic healing at Week 12.
- Mucosal healing at Week 12 (Composite Mayo endoscopic healing and histologic healing).
- Change from baseline in the total score of the Inflammatory Bowel Disease Questionnaire (IBDQ) at Weeks 6 and 12.
- A >20 -point improvement in the IBDQ score at Weeks 6 and 12.
- Change from baseline in the 7 domains and the abdominal pain numerical rating scale of Patient-Reported Outcomes Measurement Information System (PROMIS)-29 at Weeks 6 and 12.
- Fatigue response at Weeks 6 and 12 (based on the PROMIS Fatigue Short Form 7a; to be defined in the SAP).
- Clinical response, clinical remission, and endoscopic healing at Week 12 by negative response signature status at baseline.
- Change from baseline in the Mayo score at Week 12.

- Change from baseline in the partial Mayo score through Week 12.
- Change from baseline in CRP through Week 12.
- Change from baseline in fecal calprotectin concentration through Week 12.
- Normalization of CRP concentration at Week 12 among participants with abnormal CRP concentration at baseline.
- Normalization of fecal calprotectin concentration at Week 12 among participants with abnormal fecal calprotectin concentration at baseline.
- Ulcerative Colitis Endoscopic Index of Severity (UCEIS) score at Weeks 0 and 12 by the level of Mayo endoscopy score at the corresponding visit.
- Change from baseline in the UCEIS score at Week 12.
- UCEIS score ≤ 4 at Week 12.
- UC-related emergency department visits, hospitalizations, and surgeries through Week 12.

Monotherapy Phase (ie, after Week 12)

- Clinical remission at Week 38.
- Clinical response at Week 38.
- Maintenance of clinical response at Week 38 among participants who achieved clinical response at Week 12.
- Endoscopic healing at Week 38.
- Normalization of endoscopic appearance of the mucosa at Week 38.
- Histologic healing at Week 38.
- Mucosal healing at Week 38.
- Clinical remission and not receiving concomitant corticosteroids at Week 38.
- Maintenance of clinical remission at Week 38 among participants who achieved clinical remission at Week 12.
- Change from baseline in the total score of the IBDQ at Weeks 24 and 38.
- A >20-point improvement in the IBDQ score at Weeks 24 and 38.

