9.4.1.4. Other Efficacy Endpoint Analyses

Pairwise comparisons of the combination therapy with each monotherapy will be made for the endpoints specified in Section 3.2.3 with details that are to be specified in the SAP.

All statistical testing will be performed at the 1-sided 0.1 significance level. No adjustments for multiple comparisons will be made for these other efficacy endpoints and nominal p-values will be presented.

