5.5. Other Efficacy Endpoints

In addition to the primary and major secondary endpoints, other efficacy endpoints related to disease status, HRQoL outcomes (including fatigue), and inflammatory biomarkers will also be analyzed. This section outlines the definitions (Section 5.5.1) and analyses (Section 5.5.2) of the other efficacy endpoints.

Clinical Endpoints

- Clinical response at Week 38

-
- Clinical response at Week 38 by clinical response status at Week 12
 - Clinical remission at Week 38
 - Clinical remission at Week 38 by clinical remission status at Week 12
 - Clinical remission at Week 38 by clinical response status at Week 12
 - Change from baseline in Mayo score at Weeks 12 and 38.
 - Change from baseline in partial Mayo score by visit through Week 38.
 - Change from baseline in modified Mayo score at Weeks 12 and 38.
 - Change from baseline in Mayo subscores by visit through Week 38.
 - Modified Mayo response at Weeks 12 and 38
 - Modified Mayo response at Week 38 by modified Mayo response status at Week 12
 - Symptomatic remission by visit through Week 38
 - Endoscopic healing at Weeks 12 and 38
 - Endoscopic healing at Week 38 by endoscopic healing status at Week 12
 - Endoscopic normalization at Weeks 12 and 38.
 - Endoscopic normalization at Weeks 38 by endoscopic normalization status at Week 12
 - Clinical response, clinical remission, and endoscopic healing at Weeks 12 and 38 by negative response signature status at baseline.
 - Clinical remission by alternative definitions:
 - Clinical remission (UNIFI definition) at Weeks 12 and 38
 - Clinical remission (UNIFI definition) at Week 38 by clinical remission (UNIFI definition) status at Week 12
 - Clinical remission (Health Authority definition 1) at Weeks 12 and 38
 - Clinical remission (Health Authority definition 1) at Week 38 by clinical remission (Health Authority definition 1) status at Week 12
 - Clinical remission (Health Authority definition 2) by visit at Weeks 12 and 38
 - Clinical remission (Health Authority definition 2) at Week 38 by clinical remission (Health Authority definition 2) status at Week 12
 - Histologic healing at Weeks 12 and 38
 - Mucosal healing at Weeks 12 and 38
 - Histologic remission at Weeks 12 and 38
 - Histologic-endoscopic mucosal healing at Weeks 12 and 38
 - Deep histologic-endoscopic mucosal healing at Weeks 12 and 38
 - Geboes total score, high activity subscore, and low activity subscore at Weeks 0, 12, and 38

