5.5.3. Estimators (Analyses) for Estimands

Unless otherwise specified, the other endpoints presented in Section 5.5 will be analyzed based on the FAS (Section 2.2.2) according to randomized study intervention regardless of the study intervention actually received.

Descriptive statistics (i.e., mean, median, SD, IQ range, minimum, and maximum) will be used to summarize continuous endpoints and counts and percentages will be used to summarize binary endpoints by visit.

Treatment comparisons between combination therapy versus each monotherapy will be performed by visit through Week 38. All statistical testing will be performed at the 2-sided significance level of 0.2. No adjustment for multiple comparisons will be made for these other endpoints. Nominal p-values will be presented.

Binary Endpoints

After accounting for the ICEs, participants with missing status for a binary endpoint will be considered not to have achieved the associated binary endpoint (i.e. nonresponder imputation).

Binary endpoints will be summarized with the number and frequency of participants who achieve the endpoint by treatment group. Treatment comparisons (combination therapy versus each monotherapy) will be performed using analyses suitable for categorical data (e.g., a CMH chi-square test stratified by corticosteroid use at baseline, as appropriate) to compare the proportion of participants achieving the endpoints. In case of rare events, the Fisher's exact test will be used for treatment comparisons.

Continuous Endpoints

For continuous endpoints that are assessed only at one post-baseline visit (e.g., change from baseline in Mayo score and change from baseline in modified Mayo score at the Week 12 DBL), the missing data after accounting for ICEs will be imputed by the MI methods as described in [Table 3](#). The MI will be performed on each Mayo subscore with missing data and then the Mayo scores will be derived from such imputed subscores. These endpoints will be compared between combination therapy versus each monotherapy using an analysis of covariance (ANCOVA) with treatment group, corticosteroid use at baseline (yes, no), and baseline score as the explanatory factors.

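### The Week 38 maintenance tables compare arms within groups defined by Week 12 outcome, so these between-arm p-values are not protected by randomisation, and no durability endpoint uses the full FAS

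*SAP*

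**What the plan says.** SAP 5.5 includes "Clinical response at Week 38 by clinical response status at Week 12" and "Clinical remission at Week 38 by clinical remission status at Week 12". Nine further Week 38 endpoints are built the same way: remission by Week 12 response, modified Mayo response, endoscopic healing, endoscopic normalization, three alternative remission definitions, and corticosteroid-free response and remission. That makes 11.

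Protocol 3.2.3 words two of these with an explicit denominator: "Maintenance of clinical response at Week 38 among participants who achieved clinical response at Week 12" and "Maintenance of clinical remission at Week 38 among participants who achieved clinical remission at Week 12".

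On testing, Protocol 9.4.1.4 states: "Pairwise comparisons of the combination therapy with each monotherapy will be made for the endpoints specified in Section 3.2.3". SAP 5.5.3 states: "Treatment comparisons between combination therapy versus each monotherapy will be performed by visit through Week 38". It continues: "All statistical testing will be performed at the 2-sided significance level of 0.2", and "No adjustment for multiple comparisons will be made for these other endpoints. Nominal p-values will be presented". Neither document excludes the endpoints split by Week 12 status. Elsewhere the SAP does write such exclusions: Section 4 (subject information) and Section 6 (safety) both rule out formal comparisons.

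The only randomisation is at Week 0 (SAP 1.2). After Week 12 the combination arm continues on guselkumab alone, and each monotherapy arm continues its own drug.

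SAP 5.5 also lists Week 38 response, remission, endoscopic healing and endoscopic normalization without conditioning. SAP 5.5.3 analyses these in the FAS as randomised, with nonresponder imputation.

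**The concern.** Week 12 response is the primary endpoint, and the trial is sized on the expectation that treatment changes it. Participants who respond on the combination are then not the same kind of group as those who respond on a monotherapy. If the combination brings in extra responders whose response is less durable, its responder subset starts with a poorer outlook. If those extra responders are more durable, the subset starts with a better one. Complete follow-up does not remove the problem, because it comes from who is in the denominator.

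A secondary objective (Protocol 3.1.2) is the efficacy of combination therapy followed by guselkumab, and Protocol 4.3.3 asks how guselkumab performs as maintenance after combination induction. The split tables are where a reader will look for durability. With two comparators, 11 endpoints can give up to 22 nominal p-values in the Week 12 achievers alone. No listed endpoint measures achievement at both Week 12 and Week 38 in all FAS participants, so durability has no randomised comparison of its own.

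**Working it through.** **1. The plan's own figure.** SAP Table 1 gives 81% power to win both comparisons at 55%, 55% and 75% response, with 70 per arm and 1-sided 0.1 for each test. Simulating two chi-square tests that share one combination arm (400,000 runs, no continuity correction) gives 81.4%. The other five rows also reproduce within 1 point (79.2, 65.7, 69.1, 89.8 and 85.3 against 79, 66, 69, 90 and 85). The Week 12 rates can be used as design inputs.

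**2. Size of the Week 12 responder groups (SAP 1.4).** Combination: 0.75 × 70 = 52.5. Each monotherapy: 0.55 × 70 = 38.5. The groups differ by design.

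**3. Assumptions for Week 38.** The documents give no Week 38 rates, so everything here is illustrative.
- 55% of participants would respond at Week 12 on either regimen, and 80% of them still respond at Week 38, the same in both arms.
- A further 20% respond at Week 12 only on the combination, and keep response with probability q.
- The remaining 25% do not respond at Week 12 on either.
- Late response (at Week 38 but not at Week 12) is 10%.

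**4. Formulas.**
- Responder subset: combination (0.55 × 0.80 + 0.20 × q) / 0.75; monotherapy 0.80.
- FAS at Week 38: combination 0.55 × 0.80 + 0.20 × q + 0.25 × 0.10; monotherapy 0.55 × 0.80 + 0.20 × 0.10 + 0.25 × 0.10 = 48.5%.
- Both weeks, FAS: combination 0.55 × 0.80 + 0.20 × q; monotherapy 0.55 × 0.80 = 44%.

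**5. Results (combination versus monotherapy, difference in points).**

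| q | Week 12 responders only | FAS, Week 38 | FAS, both weeks |
|---|---|---|---|
| 0.8 | 80.0% v 80.0% (0) | 62.5% v 48.5% (+14) | 60% v 44% (+16) |
| 0.7 | 77.3% v 80.0% (-2.7) | 60.5% v 48.5% (+12) | 58% v 44% (+14) |
| 0.6 | 74.7% v 80.0% (-5.3) | 58.5% v 48.5% (+10) | 56% v 44% (+12) |
| 0.5 | 72.0% v 80.0% (-8.0) | 56.5% v 48.5% (+8) | 54% v 44% (+10) |
| 0.4 | 69.3% v 80.0% (-10.7) | 54.5% v 48.5% (+6) | 52% v 44% (+8) |

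The subset difference is 0.20 × (q − 0.80) / 0.75. It is zero at equal durability and changes sign above it: q = 0.9 gives 0.20 × 0.10 / 0.75 = +2.7 points. The FAS Week 38 difference is 0.20 × (q − late response rate). Varying the late rate in the 20% group from 0 to 20% widens the FAS range to +4 (q = 0.4, late 20%) through +16 (q = 0.8, late 0).

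**6. How often it would show.** Simulation of 200,000 trials, 70 per arm, with an unstratified 2-sided 0.2 test in Week 12 responders:
- q = 0.5: combination behind in 81% of trials, nominally significant against it in 35%.
- q = 0.7: 62% and 17%.
- q = 0.8: 50% and 10%, which is the chance level.

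**The case against.** - **The randomised Week 38 comparison is already planned.** This stands. Unconditional Week 38 endpoints in the FAS address the stated objective directly. A reader might infer that the plan cannot validly assess combination induction followed by guselkumab; the documents do not support that.
- **The SAP does not say it tests within responders.** This stands in part. Splitting by status with the FAS as default population gives no denominator. A responder or remitter denominator is explicit only in Protocol 3.2.3, and only for response and remission. Some items in the same SAP list, such as missing Mayo score by reason, read as descriptive tables. But Protocol 9.4.1.4 does apply pairwise comparisons to the two maintenance endpoints, and SAP 5.5.3 exempts nothing.
- **The bias is hypothetical.** Its size and sign are. A reader might infer that the combination will look worse at maintenance, but that needs less durable extra responders, and the documents have no data on this. The illustration also assumes that every monotherapy responder would respond on the combination and hold response equally well. Combination participants lose golimumab at Week 12 while the golimumab arm keeps it, so lower retention could be a real withdrawal effect. The split table cannot separate that from selection.
- **A sustained rate can be read off the split table.** True: the count with both outcomes divided by the FAS number gives it. It is not named as an endpoint or compared, however.
- **The stakes are low.** This stands. These are non-primary endpoints with unadjusted nominal p-values in a Phase 2a study, and the success rule uses Week 12 response only.

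**Conclusion.** The point holds within limits. Followed as written, the plan produces between-arm p-values in groups formed after randomisation by an outcome that treatment is expected to change. Those comparisons lack the protection of randomisation and may be biased either way. Under the stated assumptions the responder-subset difference is -10.7 to 0 points while the FAS Week 38 difference is +6 to +14. These figures show what can happen and do not forecast this trial. The primary analysis, the major secondary analysis and the unconditional Week 38 comparisons are unaffected. The gap is in durability, where the listed endpoints offer only the conditional tables. It is an inexpensive improvement and does not threaten the trial's main conclusion.

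**What to change.** In SAP 5.5 and 5.5.3:

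1. Keep the unconditional Week 38 comparisons in the FAS as planned.
2. Add clinical response, clinical remission and endoscopic healing at both Week 12 and Week 38, with all FAS participants as denominator and the intercurrent-event and nonresponder rules already set for binary endpoints. Make these the compared durability endpoints.
3. State the denominator of each table split by Week 12 status, and report those tables descriptively without between-arm p-values.
4. Record item 3 as a change from Protocol 9.4.1.4.

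The cost is SAP wording, a few derived flags and a documented departure from the protocol; no new data are needed. Nominal p-values for the conditional tables are lost. The sustained endpoint gives no credit to participants who first respond after Week 12, so it should sit beside the unconditional Week 38 endpoints and not replace them.

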5.1. Inclusion Criteria

Each potential participant must satisfy all of the following criteria to be enrolled in the study:

1. Male or female, 18 to 65 years old (inclusive).
2. Has a confirmed clinical diagnosis of UC at least 3 months before screening.
3. Has moderately to severely active UC, defined as a baseline (Week 0) Mayo score of 6 to 12, inclusive, using the Mayo endoscopy subscore obtained during the central review of the video endoscopy.
4. Has a screening endoscopy with ≥ 2 endoscopy subscore of the Mayo score as obtained during the central review of the video endoscopy.

Concomitant or previous medical therapies received

5. Must be naïve to TNF antagonists and have a prior or current UC medication history that includes at least 1 of the following:
 - a. Inadequate response to or failure to tolerate current treatment with oral corticosteroids or immunomodulators (6-MP or AZA) as defined in Appendix 2 (Section 10.2).

OR

 - b. History of failure to respond to, or tolerate, at least 1 of the following therapies: oral or IV corticosteroids or immunomodulators (6-MP or AZA) as defined in Appendix 2 (Section 10.2).

OR

 - c. History of corticosteroid dependence (ie, an inability to successfully taper corticosteroids without a return of the symptoms of UC) as defined in Appendix 2 (Section 10.2).
6. Before the first administration of study intervention, the following conditions must be met:
 - a. If receiving oral 5-aminosalicylic acid (5-ASA) compounds, the dose must have been stable for at least 2 weeks.
 - b. If receiving oral corticosteroids other than budesonide or beclomethasone dipropionate, the dose must be ≤ 20 mg/day prednisone or its equivalent and must have been stable for at least 2 weeks.

- c. If receiving budesonide or beclomethasone dipropionate, the dose must have been stable for at least 2 weeks.
 - d. If oral 5-ASA compounds or oral corticosteroids have been recently discontinued, they must have been stopped for at least 2 weeks.
7. The following medications/therapies must have been discontinued before the first administration of study intervention:
 - a. Immunomodulators (6-MP, AZA, or MTX) for at least 2 weeks.
 - b. Vedolizumab for at least 18 weeks.
 - c. Tofacitinib and other inhibitors of JAKs for at least 4 weeks or 5 half-lives, whichever is longer.
 - d. Cyclosporine, mycophenolate mofetil, tacrolimus, or sirolimus for at least 4 weeks.
 - e. 6-thioguanine must have been discontinued for at least 4 weeks.

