 - Roberts Histologic Index (RHI)-based histologic remission at Weeks 12 and 38

-
- Nancy Histologic Index (NHI)-based histologic remission at Weeks 12 and 38
 - Ulcerative Colitis Endoscopic Index of Severity (UCEIS) score at Weeks 0, 12, and 38 by the level of Mayo endoscopy score at the corresponding visit
 - Change from baseline in UCEIS score at Weeks 12 and 38
 - UCEIS score ≤ 4 at Weeks 12 and 38
 - Clinical remission and not receiving concomitant corticosteroids at Week 12
 - Clinical response and not receiving concomitant corticosteroids at Week 12
 - Clinical remission and not receiving concomitant corticosteroids at Week 38
 - Clinical response and not receiving concomitant corticosteroids at Week 38
 - Clinical remission and not receiving concomitant corticosteroids at Week 38 by status of clinical remission and not receiving concomitant corticosteroids at Week 12
 - Clinical response and not receiving concomitant corticosteroids at Week 38 by status of clinical response and not receiving concomitant corticosteroids at Week 12
 - ICEs (listed in Section 5.3.2) prior to Week 12 and prior to Week 38
 - Mayo score missing at Week 12 by reason causing missing (including COVID-19 related) and at Week 38 by reason causing missing (including COVID-19 related)
 - Endoscopy subscore missing at Week 12 by reason causing missing (including COVID-19 related) and at Week 38 by reason causing missing (including COVID-19 related)

Inflammatory Biomarkers (CRP and Fecal Calprotectin)

- Change from baseline in CRP by visit through Week 38
- Change from baseline in CRP by visit through Week 38 among participants with abnormal CRP concentration at baseline
- Change from baseline in fecal calprotectin concentration by visit through Week 38
- Change from baseline in fecal calprotectin concentration by visit through Week 38 among participants with abnormal fecal calprotectin concentration at baseline
- Normalization of CRP concentration by visit through Week 38 among participants with abnormal CRP concentration at baseline
- Normalization of fecal calprotectin concentration by visit through Week 38 among participants with abnormal fecal calprotectin concentration at baseline

HRQoL Endpoints

- Change from baseline in the total score of the Inflammatory Bowel Disease Questionnaire (IBDQ) by visit through Week 38
- A >20-point improvement from baseline in the IBDQ score by visit through Week 38

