- Change from baseline in the 7 domain scores (norm-based) and the abdominal pain intensity score of Patient-Reported Outcomes Measurement Information System (PROMIS)-29 by visit through Week 38

- A ≥ 5 -point improvement from baseline in PROMIS-29 domain scores (norm-based) and pain intensity score by visit through Week 38
- Change from baseline in the PROMIS Fatigue Short Form 7a total score by visit through Week 38
- Fatigue response (≥ 5 -point improvement) based on the PROMIS Fatigue Short Form 7a by visit through Week 38

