5.5.1.3.2. PROMIS-29

The **PROMIS-29** is a validated general health profile instrument that is not disease-specific. It is a collection of short forms containing 4 items for each of 7 domains (depression, anxiety, physical function, pain interference, fatigue, sleep disturbance, and ability to participate in social roles and activities). PROMIS-29 also includes an overall average pain intensity 0-10 numeric rating scale. Norm-based scores have been calculated for each domain on the PROMIS measures, with a score of 50 representing the mean or average of the reference population. On symptom-oriented domains of PROMIS-29 (anxiety, depression, fatigue, pain interference, and sleep disturbance), higher scores represent worse symptomatology. On the function-oriented domains (physical functioning and social role), higher scores represent better functioning.

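### One 5-point responder cut-off covers both the norm-based PROMIS-29 domains and the raw 0-10 pain item, so participants with baseline pain of 0 to 4 cannot respond on pain

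*SAP*

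**What the plan says.** In SAP 5.5, the HRQoL list sets a responder endpoint of at least a 5-point "improvement from baseline in PROMIS-29 domain scores (norm-based) and pain intensity score by visit through Week 38". One number governs two kinds of score.

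SAP 5.5.1.3.2 describes them differently. For the domains: "Norm-based scores have been calculated for each domain on the PROMIS measures, with a score of 50 representing the mean or average of the reference" … For pain: "PROMIS-29 also includes an overall average pain intensity 0-10 numeric rating scale". Protocol 8.1.6 says the same. In the responder bullet, the norm-based label is attached to the domain scores only. Neither document gives pain a cut-off of its own.

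On the analysis, SAP 5.5.3 states that "the other endpoints presented in Section 5.5 will be analyzed based on the FAS (Section 2.2.2) according to randomized study intervention", and that "participants with missing status for a binary endpoint will be considered not to have achieved the associated binary endpoint (i.e. nonresponder imputation"). No minimum baseline pain is set for the endpoint. Eligibility sets none either: Protocol 5.1, criterion 3, reads "Has moderately to severely active UC, defined as a baseline (Week 0) Mayo score of 6 to 12, inclusive". None of the four Mayo subscores is a pain score, although the physician's global assessment takes abdominal discomfort into account.

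The SAP does restrict by baseline level elsewhere, for example: "Normalization of CRP concentration by visit through Week 38 among participants with abnormal CRP concentration at baseline".

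Protocol 3.2.3 lists only change from baseline for PROMIS-29, and it calls the item "the abdominal pain numerical rating scale of Patient-Reported Outcomes Measurement Information System".

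**The concern.** A cut-off has meaning only relative to the scale it is applied to. Five points may suit a score centred on 50, but it is half the full range of a 0-10 item. Participants who enter with little pain cannot improve by that much, so they are counted as failures whatever the treatment does. The reported pain responder rate then partly reflects how many participants started with low pain, and the absolute difference between arms is diluted. At stake is how readable and sensitive this one endpoint is. A programmer following the bullet as written would apply 5 points to the pain item.

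**Working it through.** The plan states no expected rate, effect or power for this endpoint, so there is no figure of its own to reproduce.

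**Inputs from the documents.** Cut-off of at least 5 points (SAP 5.5); pain scale 0 to 10 (SAP 5.5.1.3.2, Protocol 8.1.6); FAS with non-responder imputation, tested at 2-sided 0.2 (SAP 5.5.3); 70 participants planned per arm (SAP 1.4).

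**Step 1: who can respond.** Improvement = baseline − follow-up, and follow-up is at least 0. The largest possible improvement is therefore the baseline value, and a 5-point improvement needs a baseline of at least 5.

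| Baseline pain | Follow-up needed | Smallest qualifying reduction |
|---|---|---|
| 0, 1, 2, 3, 4 | impossible | – |
| 5 | 0 | 5/5 = 100% |
| 6 | ≤1 | 5/6 = 83.3% |
| 7 | ≤2 | 5/7 = 71.4% |
| 8 | ≤3 | 5/8 = 62.5% |
| 9 | ≤4 | 5/9 = 55.6% |
| 10 | ≤5 | 5/10 = 50% |

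Five of the 11 scale values are excluded by construction. For comparison, the IBDQ cut-off of more than 20 points is about 20/(224 − 32) = 10.4% of its range; the pain cut-off is 5/10 = 50%.

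**Step 2: effect on the rate and the difference.** Let f be the share with baseline pain below 5, equal in the two arms, and let p₁ and p₂ be the response rates among the rest.

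- FAS rates: (1 − f)p₁ and (1 − f)p₂, each at most 1 − f.
- FAS difference: (1 − f)(p₁ − p₂).
- FAS ratio: p₁/p₂, unchanged.

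**Step 3: illustration.** Neither f nor the response rates are in the documents. Assume p₁ = 60% and p₂ = 40%, a 20-point difference, and f between 0.3 and 0.7. Power is Φ[(Δ − z₀.₉·SE₀)/SE₁], with SE₀ pooled and SE₁ unpooled. The FAS column uses 70 per arm. The last column uses only participants with baseline of at least 5.

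| f | Cap on rate | FAS rates | FAS difference | FAS power | Power, baseline ≥5 only (n per arm) |
|---|---|---|---|---|---|
| 0.3 | 70% | 42% vs 28% | 14 points | 0.677 | 0.762 (49) |
| 0.5 | 50% | 30% vs 20% | 10 points | 0.534 | 0.655 (35) |
| 0.7 | 30% | 18% vs 12% | 6 points | 0.386 | 0.506 (21) |

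With f = 0, power would be 0.866. Restricting the analysis recovers only part of the loss (0.085, 0.121 and 0.120 respectively), because it also reduces the sample.

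**The case against.** The strongest reply concerns consequence, and most of it stands.

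- **A reader might infer that a real pain benefit would be reported as absent.** The documents do not support this. The bullet just before the responder bullet analyses change from baseline in the same item. Under SAP 5.5.3 that analysis is an MMRM giving a least-squares mean difference and an 80% CI. Pain interference is one of the seven domains and has both change and responder analyses. Abdominal pain also enters the IBDQ bowel dimension.
- **A reader might infer a biased comparison.** Pain is rated before treatment, so randomisation makes the expected share of low-baseline participants equal across arms. The test remains valid, and the ratio of response rates is preserved. What is lost is absolute difference and power. The endpoint can still be read as the proportion of all treated participants with a large pain reduction.
- **Other responder endpoints have range limits too.** A gain of more than 20 on an IBDQ capped at 224 is impossible from a baseline of 204 or above. A drop of 2 loose stools per day is impossible for anyone averaging fewer than 2. This is fair, but those cut-offs were set for their own scales. The pain cut-off shares its number with scores on a different scale.
- **The sponsor may have meant 5 points for the domains only.** Possibly, but the bullet names both scores.

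**Conclusion.** The point holds as a scale mismatch with a built-in floor, and it is minor. That baselines of 0 to 4 cannot respond follows from the text and from arithmetic, with no outside threshold needed. The cap of 1 − f is equally firm. The shrinkage of the difference by 1 − f also requires f to be the same in each arm.

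The size in this trial is unknown. The range of 14 to 6 points and the power figures rest on assumed values of f, an assumed 20-point difference and assumed rates of 60% and 40%. They should not be read as estimates.

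The endpoint is one of many other efficacy endpoints with nominal, unadjusted p-values. It was added in the SAP and has no bearing on whether the study is declared positive.

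**What to change.** Remove the pain item from the 5-point responder bullet in SAP 5.5 and rely on its planned change-from-baseline analysis. No protocol endpoint is lost, because Protocol 3.2.3 asks only for change.

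If a pain responder endpoint is wanted, give it its own cut-off, justified for a 0-10 scale. Limit it to participants whose baseline permits that improvement, and state the denominator. Restricting to baseline of at least 5 while keeping the 5-point rule removes the impossible cases but leaves the mismatched cut-off: a baseline of 5 would still have to fall to 0.

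Separately, reconcile the item's label. Protocol 3.2.3 and the change-from-baseline bullet in SAP 5.5 call it abdominal pain, while Protocol 8.1.6 and SAP 5.5.1.3.2 describe a rating of overall pain.

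The cost is limited to wording: the SAP for the responder rule, and both documents for the label. The downside is that one SAP-added responder analysis is dropped or has a smaller denominator.
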